3.4 MEDICATION CONSIDERATIONS

3.4.A SYMPTOM MONITORING

The study staff (research clinicians [addiction physicians with extensive experience performing pharmacotherapy trials]) will provide participants with the correct medication packages and advice on how to take the capsules. The staff will be trained to assess for adverse medication effects and will follow established protocols for identifying and monitoring any ongoing adverse events, including referral to treatment as appropriate. Study participants will be actively monitored for adverse events. Symptoms will be assessed every two weeks (and monitored more frequently, if necessary) by trained clinical staff, while the participants are administered study medications. Processes have be set up to address any adverse event brought to the attention of study staff during the trial.

3.4.B. ADHERENCE

As one of the study outcomes, medication adherence will be assessed at each study visit using the following measures.

Capsule Counts

Participants will be instructed to bring any unused medication to each study visit post-baseline. The RA will count and record the number of remaining capsules. We will extrapolate the amount of medication taken and determine the measure of adherence.

Self-Report

Medication adherence will also be measured through self-report using the modified Adult AIDS Clinical Trial Group (AACTG) ART adherence questions.

Pill Diary

Participants will be asked to keep a daily written record ("daily diary") of pain severity, medication adherence, and alcohol use.

Adherence Aids

During each study visit medication instructions will be reviewed and strategies for adherence discussed with each participant. Adherence plans will be individually tailored to each participant, depending on his or her reason for non-adherence.

Participants will also be encouraged to set a reminder in their phone to take the study medication three times each day.

3.4.C. MEDICATION DISBURSEMENT

Medication inserts will be provided to participants at baseline.

Medication distribution will be as follows:

Naltrexone:

- 7 capsules/box, 1 capsule/day (Week 1)
 - o Week 1: 4.5 mg qd (4.5 mg total)
- 21 capsules/box, 3 capsules/day (Week 2)
 - Week 2: 4.5 mg naltrexone qd, 1 placebo capsule bid
- 42 capsules/box, 6 capsules/day (Week 3-7)
 - Weeks 3-7: 1 placebo to be taken with 4.5 mg naltrexone qd, 2 placebo capsules to be taken bid
- 33 capsules/box, (Week 8)
 - Days 1-4 (6 capsules/day): 1 placebo to be taken with 4.5 mg naltrexone qd, 2 placebo capsules to be taken bid
 - o Days 5-7 (3 capsules/day): 4.5 mg naltrexone qd, 1 placebo capsule bid
- Participants will receive 1 box of 7 capsules and 1 box of 21 capsules at baseline (14 days' worth).
- Participants will receive 1 box of 42 capsules at week 1 (7 days' worth).
- Participants will receive 2 boxes of 42 capsules at week 2 (14 days' worth).
- Participants will receive 2 boxes of 42 capsules at week 4 (14 days' worth).
- Participants will receive 1 box of 33 capsules at week 6 (7 days' worth).

Gabapentin:

- 7 capsules/box, 1 capsule/day (Week 1)
 - Week 1: 300 mg qd (300mg total)
- 21 capsules/box, 3 capsules/day (Week 2)
 - o Week 2: 300 mg tid (900 mg total)
- 42 capsules/box, 6 capsules/day (Week 3-7)
 - Weeks 3-7: 2 capsules of 300 mg tid (1800 mg total)
- 33 capsules/box (Week 8)
 - o Days 1-4 (6 capsules/day): 2 capsules of 300 mg tid (1800 mg total)
 - o Days 5-7 (3 capsules/day): 300 mg tid (900 mg total)
- Participants will receive 1 box of 7 capsules and 1 box of 21 capsules at baseline (14 days' worth).
- Participants will receive 1 box of 42 capsules at week 1 (7 days' worth).
- Participants will receive 2 boxes of 42 capsules at week 2 (14 days' worth).
- Participants will receive 2 boxes of 42 capsules at week 4 (14 days' worth).
- Participants will receive 1 box of 33 capsules at week 6 (7 days' worth).

Placebo:

- 7 capsules/box, 1 capsule/day (Week 1)
 - o Week 1: 1 placebo capsule qd
- 21 capsules/box, 3 capsules/day (Week 2)
 - Week 2: 1 placebo capsule tid
- 42 capsules/box, 6 capsules/day (Week 3-7)

- Weeks 3-7: 2 placebo capsules tid
- 33 capsules/box (Week 8)
 - o Days 1-4 (6 capsules/day): 2 placebo capsules tid
 - o Days 5-7 (3 capsules/day): 1 placebo capsule tid
- Participants will receive 1 box of 21 capsules and 1 box of 42 capsules at baseline (14 days' worth).
- Participants will receive 1 box of 42 capsules at week 1 (7 days' worth).
- Participants will receive 2 boxes of 42 capsules at week 2 (14 days' worth).
- Participants will receive 2 boxes of 42 capsules at week 4 (14 days' worth).
- Participants will receive 1 box of 33 capsules at week 6 (7 days' worth).

Medication boxes will also be labeled. The medication labels will contain the following information:

FOR CLINICAL TRIAL USE ONLY

NALTREXONE/GABAPENTIN/PLACEBO

STORAGE: Don't store medication above 25°C.

KEEP OUT OF REACH OF CHILDREN AND PETS.

Return all unused medication to the study site.

DATE OF MANUFACTURE:

SHELF LIFE:

3.4.D. LOST OR STOLEN STUDY MEDICATION

If participants report lost or stolen medication, they will be provided with extra study medication. If participants report losing medication more than once, the study team will be alerted and the case discussed to determine a plan of action.

3.4.E. DISCONTINUATION OF STUDY MEDICATION

If as a result of study testing at week 4, a participant is found to have AST/ALT >10x normal, medications will be discontinued and the participants will be appropriately monitored for resolution of the abnormalities. If a participant has AST/ALT >5x normal as a result of study testing at week 4, participant will be rechecked at their 6-week visit to ensure levels do not increase to the threshold of discontinuation. Any participant with symptoms of acute hepatic failure (jaundice, dark urine) will have AST/ALT checked.

Those who discontinue medication will be followed and analyzed by intention to treat.

Participants found to be pregnant during the study will have their study medication discontinued, but will still be followed-up for the duration of the study. Participants who report pregnancy outside of study

visits will be instructed to immediately discontinue their study medication and requested to come in for a confirmatory urine pregnancy test.

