2.3 STUDY DESIGN

This is a randomized, double-blinded, 3-arm study of 45 participants with HIV, chronic pain (defined as any bodily pain of moderate to severe intensity lasting for ≥3 months), and past-year heavy alcohol use, defined by NIAAA criteria. The 45 participants will be randomly assigned to either naltrexone, gabapentin, or placebo, using permuted blocks, to ensure equal numbers in each arm. Patients and research staff will be blinded to randomization. Participants will be treated for 8 weeks, and then assessed for an additional 4 weeks post-treatment.

The study design and schedule for study visits and assessments is depicted in Figure 1. After consent and enrollment, participants will be randomly assigned to receive either low-dose naltrexone, gabapentin, or placebo. Participants will be randomized using permuted blocks, to ensure similar numbers within each arm. Patients and research staff will be blinded to randomization. Participants will be given 2 weeks of medication at baseline, 2-weeks, 4-weeks, and 6-week visits, with instructions to bring pill packs/leftover medications to the following visit. The schedule of study visits is as follows: baseline (pre-treatment), week 4 (on treatment), week 8 (on treatment), week 12 (post-treatment). At the 8 week visit, all assessments will occur (see Section 5). At week 4, we will assess for medication tolerability, discontinuation, treatment side effects, self-reported adherence to intervention medications, and pain (BPI) only. At week 12 (post-treatment), there will be an assessment of pain (BPI) and cold-pressor test to assess whether pain reverts back to pre-treatment levels. Weeks 1, 2, 6, and 7 will be short visits at which time a brief assessment of tolerability, side effects, and adherence will occur, and we will ensure that participants have their medications (e.g. have not been lost or stolen).

Figure 1: Study Design (UH3 Phase)

Page 5 of 44

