Please note that these side effects were reported among people taking 50mg of naltrexone. This study will use low dose naltrexone (4.5mg) and side effects are expected to be milder. In order to help prevent these adverse effects, participants will be instructed not to take more medication than what is provided by the study. Study clinicians will also be monitoring for signs of naltrexone overdose. These adverse effects are not expected to be likely.

3.3.B. GABAPENTIN

Participants randomized to this group will receive gabapentin for 8 weeks.

Gabapentin dosing will start on the day of the baseline visit after successful passing of the naloxone challenge. If the participant does not pass the naloxone challenge, he/she will be brought back within a week to try again.

Participants will be instructed to take the medication from one to three times daily for 8 weeks. Medication will be packaged in pill boxes. Participants will receive 1 box of 7 capsules and 1 box of 21 capsules at baseline (14 days worth of medication), at the 1-week visit participants will receive 1 box of 42 capsules, at the 2-week visit participants will receive 2 boxes of 42 capsules, at the 4-week visit participants will receive 2 boxes of 42 capsules; at the 6-week visit participants will receive 1 box of 33 capsules.

Participants randomized to the gabapentin arm begin on a dose of 300 mg daily (300 mg qd). In week 2, participants will take 300 mg of gabapentin three times daily. In week 3 the dose will be titrated up to 1800 mg daily (300 mg+300 mg tid) will remain on the dose until week 8, when they will be tapered back down to 900 mg daily (300 mg tid). In week 8, in days 1-4 participants will take 1800 mg daily (300 mg+300 mg tid); in days 5-7, participants will take 900 mg daily (300 mg of gabapentin three times daily). Gabapentin will only be titrated up as tolerated by the participant. Participants will be monitored regularly for side effects and medication tolerability (weeks 1, 2, 4, 6, and 7) If a participant experiences adverse effects while on medication, the participant's dose will be reduced down to the previous dose (or to a lower dose that the participant can tolerate). Research Assessors in this study are all trained addiction psychiatrists, with experience in clinical trials and adverse event monitoring.

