3.5 SCHEDULE OF DATA COLLECTION

		Scre en	Baseline Visit	1 week visit	2 week visit	4 week visit	6 week visit	7 week visit	8 week visit	12 week visit
Screening	Screening Questions	Х								
3	Verification of HIV, non-pregnancy, urine tox, and ALT/AST	Х								
Enrollment	Sign Informed Consent	Х								
Linemient	Complete contact information/verify numbers	Х								
	Randomization		Х							
	Clinical Values		Х			X			Χ	X
Laboratory	Pregnancy Test	Х	Х	X	Х	Х	Х	X		
	Urine Drug Test	Х	Х							
	AST, ALT	X				х	X (if indicat ed)			
	Creatinine	Х								
	Cold Pressor Test		Х			Х			Х	Х
	Naloxone Challenge		Х							
	Blood Draw (IL-6, IL- 1β, IL-10, TNF-alpha, CD4, HVL)		Х						х	
Assessment	Full Study Assessment		Х			Х			х	Х
	Short Assessment			Х	Х		Х	Х		
Intervention	Symptom Management/Adverse Events		×	X	Х	Х	Х	X	×	X
	Provide Medication Instructions		Х		Х	Х	Х			
	Give Study Medication		Х		Х	Х	Х			
	Discuss Adherence		Χ	Χ	Х	Χ	Х	Х	Χ	
	Assess Adherence			Χ	Х	Х	X	Х	Х	
Other	Provide Resource Card		Х							
	Compensate for Participation	Х	Х	Х	Х	Х	Х	Х	Х	Х
	Report Adverse Events		Х	Х	Х	Х	Х	Х	Х	Х
	Complete Tracking Forms	Х	Х	Х	Х	Х	Х	X	Х	Х

3.5.A. VISIT WINDOWS

Baseline Visit

Window open: 1 day post screening

• Target date: 3 days post screening

• Window close: 28 days post screening

Window length: 27 days

1 Week Visit

• Window open: 5 days post baseline

Target date: 7 days post baseline

• Window close: 10 days post baseline

• Window length: 5 days

2 Week Visit

Window open: 11 days post baseline

• Target date: 14 days post baseline

• Window close: 20 days post baseline

Window length: 9 days

4 Week Visit

Window open: 21 days post baseline

• Target date: 28 days post baseline

Window close: 37 days post baseline

Window length: 16 days

6 Week Visit

Window open: 38 days post baseline

• Target date: 42 days post baseline

• Window close: 45 days post baseline

• Window length: 7 days

7 Week Visit

• Window open: 46 days post baseline

• Target date: 49 days post baseline

• Window close: 52 days post baseline

Window length: 6 days

8 Week Visit

• Window open: 53 days post baseline

• Target date: 56 days post baseline

Window close: 73 days post baseline

Window length: 20 days

12 Week Visit

Window open: 74 days post baseline
Target date: 84 days post baseline
Window close: 94 days post baseline

Window length: 20 days

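### The week-4 dispensing window closes on day 37 but the capsules dispensed by then last only through day 34, and the protocol's dispensing passages disagree with one another

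*Combined protocol and SAP*

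**What the plan says.** **Dispensing, version A (3.3, 3.4.C, 4.4).** For the naltrexone and gabapentin arms 3.4.C lists "Participants will receive 1 box of 7 capsules and 1 box of 21 capsules at baseline (14 days' worth"), then "Participants will receive 1 box of 42 capsules at week 1 (7 days' worth"), then "Participants will receive 2 boxes of 42 capsules at week 2 (14 days' worth"), followed by 14 days' supply at week 4 and 7 days' at week 6. The visit flow in 4.4 also has medication given at week 1.

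**Dispensing, version B (2.3 and the 3.5 table).** Section 2.3 states: "Participants will be given 2 weeks of medication at baseline, 2-weeks, 4-weeks, and 6-week visits". The row for giving medication in the 3.5 table likewise has no mark at week 1.

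**Placebo.** The placebo list in 3.4.C gives boxes of 21 and 42 capsules at baseline; 3.3.C gives boxes of 7 and 21.

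**Windows (3.5.A).** The week-4 visit opens on day 21, has its target on day 28, and has "Window close: 37 days post baseline". The week-1, week-2 and week-6 windows close on days 10, 20 and 45.

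**Dosing.** Section 3.3.B states "Gabapentin dosing will start on the day of the baseline visit after successful passing of the naloxone challenge". After reaching 1800 mg daily in week 3, participants "will remain on the dose until week 8, when they will be tapered back down to 900 mg daily (300 mg tid"). Section 3.4.C has six capsules a day in weeks 3 to 7 in every arm.

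**Extra supply and adherence.** Section 3.4.D provides extra medication only when it is lost or stolen. Section 3.4.B counts the capsules left over and then says: "We will extrapolate the amount of medication taken and determine the measure of adherence". It names no denominator.

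**The concern.** A visit window tells the site how late a participant may come and still be on protocol. When the visit is also the only source of the next capsules, the supply in hand has to last to the close of that window. At week 4 it does not, so a participant and a site that both follow the protocol can still end up with days of no treatment in the middle of the six-capsule phase, where the text describes uninterrupted dosing.

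At stake are the exposure actually delivered, the conditions under which the week-4 measurements are taken (pain over the past week, cold pressor, AST/ALT), and the adherence figure, which 3.4.B treats as a study outcome. In a pilot meant to inform a larger trial, these should not depend on which dispensing passage a site happened to read.

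**Working it through.** **Inputs.** First dose on day 0 (3.3.B). Capsules per day: 1 on days 0–6, 3 on days 7–13, 6 from day 14 to day 52, 3 on days 53–55 (3.4.C). Window closes from 3.5.A.

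**The plan's own figures reproduce.** Baseline: 7/1 + 21/3 = 14 days. One box of 42: 42/6 = 7 days. Two boxes: 84/6 = 14 days. Last box: 4×6 + 3×3 = 33 capsules. Total dispensed: 28 + 42 + 84 + 84 + 33 = 271. Total scheduled over 56 days: 7 + 21 + 39×6 + 3×3 = 271. There is no overage.

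**Version A.** Whole days uncovered = max(0, close of next dispensing window − days covered).

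| After visit | Cumulative capsules | Days covered | Next dispensing window closes | Whole days uncovered |
|---|---|---|---|---|
| Baseline | 28 | 14 (0–13) | week 1, day 10 | 0 |
| Week 1 | 70 | 21 (0–20) | week 2, day 20 | 0 |
| Week 2 | 154 | 35 (0–34) | week 4, day 37 | 37 − 35 = 2 |
| Week 4 | 238 | 49 (0–48) | week 6, day 45 | 0 |

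A week-4 visit on day 36 leaves 36 − 35 = 1 whole day. These are 2 of the 17 days in the window (21 to 37 inclusive). Attending weeks 1 and 2 early or late within window does not move the run-out day. If the first dose is counted as day 1, supply covers days 1–35 and a day-37 visit leaves 1 whole day.

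**Version B.** Supply is 14 days at each of baseline and weeks 2, 4 and 6.
- Week-2 visit on day 20: 20 − 14 = 6 whole days uncovered.
- On-time week 2, then week 4 on day 37: 37 − 28 = 9 whole days uncovered.
- All visits on target dates: 0.

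**Placebo as printed in 3.4.C.** 63 + 42 + 84 = 189 capsules by week 2. After 28 for the first 14 days, 161/6 gives 26 full days, so 40 days are covered (0–39) and this arm would have no gap.

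**Adherence at a day-37 visit, version A, every capsule taken.** Scheduled for days 0–36: 7 + 21 + 23×6 = 166. Against capsules scheduled: 154/166 = 92.8%. Against capsules dispensed: 154/154 = 100%. For day 36 the scheduled total is 160, and 154/160 = 96.3%.

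**Carry-through to week 8.** Suppose six a day resumes on day 37. The 84 capsules then cover days 37–50, and the last box runs from day 51 (6 a day on days 51–54, 3 on day 55). By a day-56 visit, 154 + 84 + 24 + 3 = 265 of 271 capsules are taken, a shortfall of 6/271 = 2.2%.

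**The case against.** The best reply is that the gap is small and avoidable. Version A already holds a seven-day buffer beyond the week-4 target, so only a visit eight or nine days late loses a whole day, and the documents do not say how often that would happen. The primary outcome is at week 8, and the shortfall in capsules by then is about 2%. All of this stands and limits the weight of the point. It does not remove the conflict, because days 36 and 37 are declared in window and no bridging supply is described.

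Three stronger readings are tempting, but the documents do not support them.

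- *An abrupt stop followed by a full-dose restart with no tolerability check.* Resupply happens at the week-4 visit, which includes the symptom checklist and the tolerability questions (5.2.A), and 3.3.B lists week 4 among the monitoring points. A return to six capsules can be inferred from the box sizes, but no passage instructs it; what happens to dosing after a gap is not stated.
- *Adherence will read 100%.* That assumes capsules dispensed as the denominator, which 3.4.B does not say. Self-report and the daily diary could also show the gap.
- *The interruption is 6 or 9 days.* Those figures hold only if 2.3 and the 3.5 table are followed literally, against 3.3, 3.4.C and 4.4. They show what the inconsistency could cost and are not the size of the gap under 3.4.C.

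Nor does the point apply equally to everyone. A participant on a reduced dose would have capsules to spare, and the printed placebo list would leave that arm without a gap.

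**Conclusion.** The point holds as a conflict between supply and visit windows, together with an unreconciled set of dispensing passages. Under 3.4.C an in-window participant taking every capsule can miss 1 or 2 whole days (up to 12 capsules) before the week-4 visit, so the continuous weeks 3 to 7 dosing in 3.3.B and 3.4.C cannot be followed. This rests on a first dose on day 0, full dosing, and no supply beyond what is listed. The size is modest and the week-8 comparison is little affected, but the change is worth making because it prevents an interruption that the plan itself would cause. The inconsistency over week-1 dispensing matters more in practice if a site works from the schedule table.

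**What to change.** Reconcile 2.3, 3.3, 3.4.C, the 3.5 table and 3.5.A to a single dispensing schedule, including whether medication is given at week 1 and which baseline boxes the placebo arm receives. Write it so that the supply in hand lasts to the close of the next dispensing window, for example by supplying enough capsules to cover it. On the 3.4.C schedule that is 2 days × 6 = 12 extra capsules for the whole days before a day-37 visit, or 18 if day 37 itself is to be covered. The spares should be made up as complete daily sets in all arms so that the blind holds.

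Shortening the window to day 35 is not enough alone. It relabels a late visit without resupplying anyone, and it leaves days 36 and 37 in no window, since week 6 opens on day 38.

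As a minor addition, state in 3.4.B that capsule-count adherence is capsules taken divided by capsules scheduled for the days elapsed. A dispensed denominator would misread even a punctual visit: by day 28 the schedule calls for 7 + 21 + 14×6 = 112 of the 154 capsules dispensed, or 72.7% for someone who missed nothing.

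The cost is some protocol wording and a few spare capsules per participant. Any dosing rule after an interruption is for the sponsor to reconcile with 3.3.B.

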3.5 SCHEDULE OF DATA COLLECTION

		Scre en	Baseline Visit	1 week visit	2 week visit	4 week visit	6 week visit	7 week visit	8 week visit	12 week visit
Screening	Screening Questions	Х								
3	Verification of HIV, non-pregnancy, urine tox, and ALT/AST	Х								
Enrollment	Sign Informed Consent	Х								
Linemient	Complete contact information/verify numbers	Х								
	Randomization		Х							
	Clinical Values		Х			X			Χ	X
Laboratory	Pregnancy Test	Х	Х	X	Х	Х	Х	X		
	Urine Drug Test	Х	Х							
	AST, ALT	X				х	X (if indicat ed)			
	Creatinine	Х								
	Cold Pressor Test		Х			Х			Х	Х
	Naloxone Challenge		Х							
	Blood Draw (IL-6, IL- 1β, IL-10, TNF-alpha, CD4, HVL)		Х						х	
Assessment	Full Study Assessment		Х			Х			х	Х
	Short Assessment			Х	Х		Х	Х		
Intervention	Symptom Management/Adverse Events		×	X	Х	Х	Х	X	×	X
	Provide Medication Instructions		Х		Х	Х	Х			
	Give Study Medication		Х		Х	Х	Х			
	Discuss Adherence		Χ	Χ	Х	Χ	Х	Х	Χ	
	Assess Adherence			Χ	Х	Х	X	Х	Х	
Other	Provide Resource Card		Х							
	Compensate for Participation	Х	Х	Х	Х	Х	Х	Х	Х	Х
	Report Adverse Events		Х	Х	Х	Х	Х	Х	Х	Х
	Complete Tracking Forms	Х	Х	Х	Х	Х	Х	X	Х	Х

3.5.A. VISIT WINDOWS

Baseline Visit

Window open: 1 day post screening

• Target date: 3 days post screening

• Window close: 28 days post screening

Window length: 27 days

1 Week Visit

• Window open: 5 days post baseline

Target date: 7 days post baseline

• Window close: 10 days post baseline

• Window length: 5 days

2 Week Visit

Window open: 11 days post baseline

• Target date: 14 days post baseline

• Window close: 20 days post baseline

Window length: 9 days

4 Week Visit

Window open: 21 days post baseline

• Target date: 28 days post baseline

Window close: 37 days post baseline

Window length: 16 days

6 Week Visit

Window open: 38 days post baseline

• Target date: 42 days post baseline

• Window close: 45 days post baseline

• Window length: 7 days

7 Week Visit

• Window open: 46 days post baseline

• Target date: 49 days post baseline

• Window close: 52 days post baseline

Window length: 6 days

8 Week Visit

• Window open: 53 days post baseline

• Target date: 56 days post baseline

Window close: 73 days post baseline

Window length: 20 days

12 Week Visit

Window open: 74 days post baseline
Target date: 84 days post baseline
Window close: 94 days post baseline

Window length: 20 days

